6) Provide a statement of specific aims and hypotheses that serve as the basis for this protocol. Emphasize those aspects that justify the use of human subjects.

Aim 1: Investigate whether Computerized Executive Function Training (CEFT) leads to objective and subjective improvements in executive functioning and whether this in turn mediates PTSD symptom improvement.

Hypothesis 1a: CEFT will be associated with improvements in both objective and subjective executive functioning.

Hypothesis 1b: Enhanced executive functioning will mediate the relationship between treatment group and PTSD symptom improvement.

Aim 2: Investigate the efficacy of administering CEFT prior to Cognitive Processing Therapy (CEFT-CPT) in improving treatment adherence, completion rates, and outcomes in OEF/OIF Veterans with PTSD.

Hypothesis 2a: Individuals in the CEFT-CPT condition will have greater improvements in PTSD symptoms and quality of life than the control condition (placebo word training plus CPT).

Hypothesis 2b: Individuals in the CEFT-CPT condition will have higher rates of treatment engagement (i.e., completing more hours of homework and attending a greater number of sessions) and higher rates of treatment completion than those in the control condition.

Aim 3: Investigate whether functioning of brain regions in an EF network at baseline predicts treatment response.

Hypothesis 3: Dysfunction in a network of brain regions supporting EF will predict poorer response to treatment. Specifically, those who do not complete treatment and who demonstrate a poorer response will exhibit decreased connectivity between dorsolateral PFC and other regions, including anterior cingulate cortex and parietal cortex, compared to completers and better responders.

Section 7 - Background and Significance

7) Provide a succinct discussion of relevant background information to justify performing the proposed study.

PTSD affects approximately 14% of OEF/OIF Veterans and leads to considerable personal and societal costs (e.g., increased morbidity, reduced work productivity, poorer relationships). Cognitive behavioral therapy (CBT) has been shown to be one of the most effective treatments for PTSD. The Institute of Medicine

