Data Analysis: Data management and analysis will be supervised by [name] (Biostatistician and consultant). Data will be analyzed from all randomized subjects on whom we have a baseline assessment and at least one post-baseline evaluation. Every attempt will be made to obtain at least one follow up assessment on any individuals who drop out of treatment. Data will be screened for outliers, missing values, and violation of statistical assumptions. Preliminary analyses will be used to examine the descriptive statistics of the study sample and assess for the influence of outliers and non-normally distributed variables for possible exclusion or transformation. Gender, age, medications, depression, and TBI-related variables will be examined for differences between groups at baseline; they will be added as covariates if differences are significant.

Missing Data: Missing data values will be minimized by intensive training of the staff in techniques of clarifying answers and checking questionnaires while Veterans are on-site. When missing values are identified, several approaches to acquire the necessary data will be employed including 1) contacting the Veterans to obtain the missing data and/or 2) examining the missing data to assess randomness. We expect missing data to be randomly distributed. Missing data (i.e., loss to follow up) will be tested to determine if it is informative, and the methods developed by Diggle (1989) and Ridout (1991) to test for completely random dropouts will be applied. We will test whether the drop-outs are random or systematic by comparing the drop-outs with the study completers on the baseline data. An absence of significant differences would support the random nature of drop-outs. If the extent of missing data is small and the data appear to be consistent with a missing-at-random model (MAR), then the maximum-likelihood analysis using all randomized cases and the observed data is an appropriate method for handling the missing data.

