Analyses will be conducted using multilevel modeling (MLM; also known as hierarchical linear modeling and linear mixed effects modeling). MLM has several advantages over more traditional analytic approaches such as change scores or repeated measures ANOVAs, as it allows for the inclusion of participants who have missing data and who dropped out of the study prematurely without using data imputation or biased procedures that often reduce power, such as casewise deletion. MLM also accounts for the fact that repeated observations across time are not independent but are nested within individuals. This method can provide an estimate of the individual variability around the population trend, the variability of the individual intercepts (baseline symptom levels) and slopes (change in symptoms across time), and the correlation between them. Initial model testing will be conducted to determine whether including individual-level random effects of intercept and slope (to model variability in initial symptom level and variability in response to treatment) will improve model fit. In addition to including the significant random effects, the model will include the fixed effects of treatment group, time, and group-by-time interaction. Data will be analyzed from all randomized subjects (full intent-to-treat sample) using all available data collected at the different assessment points.

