10. The study is currently recruiting and newly enrolling, according to guidelines set forth in the VA Interim Policy on Human Subject Research During the COVID-19 Pandemic and our IRB-approved RAMP plan.

The additional protocol for remotely consenting veterans using DocuSign is as follows:

1. At the time of remote consenting, the study team member/conserver will send a DocuSign envelope (email containing links to the study documents) to the potential subject.
2. At the scheduled time, the study team member (referred to as "conserver") will contact the potential subject via VA-approved secure telehealth communication software or phone. The conserver will guide the potential subject to open the DocuSign envelope (email) and the linked study documents therein. The conserver will open a copy of the study documents on their own computer as a reference. The conserver will review the study documents with the potential subject, ask questions to gauge comprehension, and answer any questions and concerns. If the potential subject agrees to participate in the study, the conserver will guide them to fill in the fields in the study documents (e.g., "Last, First, Middle Initial" name field, Last 4 SSN field, etc.) and to sign the documents. When the subject has signed the documents, they will click "FINISH" to finalize the documents.
3. While still on the telehealth communication software or phone with the subject, the conserver will receive an email notification to log into DocuSign. The conserver will verify that all fields are completed accurately and subsequently sign the document(s) (e.g., ICF). The conserver will guide the subject on how to download a copy(ies) of the signed document(s) to the subject's personal computer for their record.
4. The conserver will download a copy(ies) of the signed document(s) to a study folder in VA network drive (i.e., R:\[name]) as study record.

Section 9.1 Clinical Procedures

9.1) Differentiate research procedures (or any procedures done for research purposes only) from clinical procedures (procedures that are done as part of standard care).

(Note: this differentiation should be clear in the consent form as well)

Research and usual care procedures: All procedures are done for research purposes. All study participants will receive Cognitive Processing Therapy (CPT) which is the standard of care for PTSD but will be delivered by study psychologist in the context of this research study.

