indirectly, any individual patient or subject in any report of such research or otherwise disclose patient or subject identities in any manner. (Ref: 38 U.S.C. 7332(b)(2)(B))

Agree Disagree

12.10f) The research could not practicably be conducted without the waiver or alteration.

Agree Disagree

12.10f2) Describe how the waiver/alteration enables the research to be conducted

The waiver will enable us to screen the patients who previously consented to be contacted for other research by accessing their CPRS file to check their eligibility for participation in this study by confirming diagnoses and therapy history. Then, a phone call will be made to those who meet the eligibility criteria. The waiver will also enable us to conduct a phone screen to prevent scheduling veterans who are ineligible to participate.

12.10g) The research could not practicably be conducted without access to and use of the PHI.

Agree Disagree

12.10g2) Describe why it would be impracticable to conduct this research without the PHI described 12.10a. (v3 /8/18)

Once we obtain a waiver, the study staff will be able to use patient's name and last four digits of the social security number to access the patient's CPRS record. Study staff will then screen patients with inclusion/exclusion criteria information in their CPRS file before making a phone call.

Section 13 - Alternatives to Participation

13) Describe the alternatives to participation in this research study (see ? for guidance)

If an individual chooses to not participate or withdraw from participation in this study, they will be offered the option to be referred to standard clinical CPT or other mental health treatment done with no research component. There may be risks associated with standard treatments for PTSD that they can review with their health care provider.

Section 14 - Potential Risks

14) Describe any potential or known risks or discomforts and assess their likelihood and seriousness (see ? for guidance)

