There is always a risk associated with the management of patients with mood and anxiety disorders that they will develop suicidality. This risk will be carefully mitigated by the systematic and careful assessment of suicidality and homicidality throughout the protocol via weekly in-session assessments made by the therapists. Subjects who develop suicidality will be evaluated by therapist, [name], and [name] to determine whether continued participation in the study is safe and clinically warranted. If the study personnel and participant feel that discontinuation would best suit the participant, the participant will be discontinued from the study, and the participant will be reviewed for appropriate treatment. All mental health staff are trained in and required by the VA to regularly assess suicidality and/or homicidality. If a patient endorses suicidal ideation or homicidal ideation, standard safety procedures are implemented via a licensed psychologist. These depend on the level of threat presented by the patient and may range from making a safety plan with the patient to implementing 5150 procedure for an inpatient hold. Homicidal ideation additionally involves assessment of whether to invoke the Tarasoff law.

For participants who wish to terminate prematurely, we will request a final meeting to assess clinical status and safety and to review reasons for withdrawal (if the participant is willing to share them). Referrals for alternative mental health services, including those in our clinics outside this protocol, will also be provided. Participants enrolled in the study may withdraw at any time without penalty or loss of any benefits or treatment options available to them. Investigators may also withdraw a participant from the study for treatment non-compliance or a newly developed psychiatric or medical problem if, in the opinion of the investigators, these factors interfere with the participant's ability to participate fully in the study. If a participant discontinues the study for any reason, he/she will be offered and allowed access to any care in our clinics that any other patient not associated with the study would receive.

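### The plan states two analysis sets without precedence; the one requiring a post-baseline evaluation would drop early leavers whose Hypothesis 2b outcome is already known

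*Combined protocol and SAP*

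**What the plan says.** All references are to the combined protocol and SAP.

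- Section 9, Data Analysis, opening paragraph: "Data will be analyzed from all randomized subjects on whom we have a baseline assessment and at least one post-baseline evaluation".
- Section 9, Data Analysis, end of the multilevel-modelling paragraph: "Data will be analyzed from all randomized subjects (full intent-to-treat sample) using all available data collected at the different assessment points". The same paragraph justifies the model because "repeated observations across time are not independent but are nested within individuals".
- Section 6, Hypothesis 2b: CEFT-CPT participants will do more homework, attend more sessions and have "higher rates of treatment completion than those in the control condition".
- Section 9.1: CPT "will be delivered by study psychologist in the context of this research study". It starts only after the six weeks of computer training (Section 9, Procedures).
- Section 13: for people who decline or withdraw, "they will be offered the option to be referred to standard clinical CPT or other mental health treatment".
- Several provisions limit how many people have no later evaluation. Section 9 plans a symptom assessment midway through training and weekly calls, and says "Every attempt will be made to obtain at least one follow up assessment on any individuals who drop out of treatment". Section 15 adds, for those wishing to stop early, that "we will request a final meeting to assess clinical status and safety".

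The plan does not say which set is primary, what counts as an evaluation, how many sessions make a completer, or which set and model apply to Hypothesis 2b.

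**The concern.** A Veteran with baseline data only is excluded by the first rule and included by the second. For the repeated symptom scores this matters little, since such a person adds almost nothing to the group-by-time estimate. Hypothesis 2b is different. Sessions attended and completion are one value per person, whereas the intent-to-treat sentence closes a paragraph about a repeated-measures model and refers to data from assessment points. An analyst could apply the opening rule to Hypothesis 2b and still be following the plan.

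That rule would treat a known failure as missing. The post-training assessment comes just before CPT, and symptoms are assessed weekly during CPT, so someone with no post-baseline evaluation will ordinarily have left before CPT began. The study delivers the therapy itself, so that person attended 0 study sessions and did not complete. This holds for study-delivered CPT only, because leavers may obtain CPT elsewhere. Homework is a separate matter: it is recorded at CPT sessions, so people who never start have no recorded value.

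At stake are an inflated completion and attendance figure in any arm with such losses, and a distorted comparison if early loss differs by arm. Because the choice between the two sets is left open, it could also be made after the data are seen.

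**Working it through.** **Inputs.** From the documents: about 150 randomised, 75 per condition (2 × 75 = 150), and 12 CPT visits. The documents give no completion rate, early-loss rate, test or significance level for Hypothesis 2b. The following are therefore assumptions: a two-sided 5% test, true completion of 50% (range 40% to 60%), and the early-loss rates shown. Early loss means no post-baseline evaluation and no completion.

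**Denominator arithmetic.** With C completers and L early leavers in an arm of 75, completion is C/75 when everyone counts and C/(75 − L) in the restricted set. Take 38 completers in each arm, with 4 early leavers in one arm and 11 in the other:

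- everyone counted: 38/75 = 50.7% in both arms, difference 0;
- restricted: 38/71 = 53.5% v 38/64 = 59.4%, so the arm that lost more people looks 5.9 points better.

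For mean sessions, give completers 12 sessions and the remaining starters 4 (an assumption):

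- arm with 4 leavers: 38×12 + 33×4 = 588 sessions, so 588/75 = 7.84 with everyone counted and 588/71 = 8.28 restricted;
- arm with 11 leavers: 38×12 + 26×4 = 560 sessions, so 560/75 = 7.47 with everyone counted and 560/64 = 8.75 restricted.

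The difference changes sign, from +0.37 to −0.47.

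With equal early loss the ratio of completion rates is unchanged, but the absolute difference is stretched. For 45 v 38 completers and 8 leavers per arm, the difference is 60.0% − 50.7% = 9.3 points with everyone counted. In the restricted set it is 45/67 − 38/67 = 10.4 points.

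**False-positive rate.** True completion p is the same in both arms. Completion among those retained is p/(1 − loss). The two binomials were enumerated exactly with a pooled two-sided z-test, averaged over the binomial number retained out of 75. With everyone counted the rate is 5.5%. In the restricted set at p = 50%:

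| Early loss, control v CEFT | Completion among retained | Rejection rate |
|---|---|---|
| 1% v 3% | 50.5% v 51.5% | 5.4% |
| 2% v 5% | 51.0% v 52.6% | 5.6% |
| 10% v 10% | 55.6% v 55.6% | 5.1% |
| 5% v 10% | 52.6% v 55.6% | 6.4% |
| 5% v 15% | 52.6% v 58.8% | 11.3% |
| 10% v 20% | 55.6% v 62.5% | 12.6% |
| 20% v 30% | 62.5% v 71.4% | 17.1% |

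For 10% v 20% loss, the rate runs from 9.7% at p = 40% to 17.8% at p = 60%. A separate normal approximation gives about 11% for 5% v 15% and about 13% for 10% v 20%.

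**The opposite case.** Suppose CEFT helps only by reducing early loss, with 65% completion among those retained in both arms. Full-sample completion is then 0.65 × (1 − loss), and the restricted set cannot show the benefit:

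| Early loss, control to CEFT | Power, everyone counted | Power, restricted |
|---|---|---|
| 3% to 1% | 5.4% | 5.1% |
| 5% to 2% | 5.9% | 5.1% |
| 10% to 5% | 7.5% | 5.1% |
| 20% to 10% | 13.7% | 5.1% |
| 25% to 10% | 23.8% | 5.1% |

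**The case against.** The strongest reply is that the intended set is clear enough. The intent-to-treat sentence comes later. The Missing Data paragraph also speaks of maximum likelihood on all randomised cases, and the modelling paragraph favours its method because it keeps people who drop out. The opening rule then looks like the outlier. This is a fair reading for the repeated symptom scores, but it does not settle Hypothesis 2b. The Missing Data statement is conditional on missingness that is small and consistent with missing at random, and both remarks concern likelihood or repeated-measures models.

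The second reply is that few people would be affected. To be dropped, a Veteran must lack the midway assessment (if it counts as an evaluation), the post-training assessment and any retrieved follow-up. Nothing in the documents suggests that loss will differ by arm; training frequency, hours, staff contact and payment are matched. This stands, and the larger loss rates above are illustrations, not forecasts.

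Third, the inflated error rates require completion among those retained to be higher in the arm with more loss, by exactly enough to equalise true completion. In the opposite case, counting everyone still leaves power of only 5.4% to 23.8%. Both points are correct. They limit the likely size of the harm, but they do not justify removing people whose result is known.

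Finally, the missing definition of completion and the missing model for it are arguably larger gaps. The scoring proposed here does not depend on that definition, since someone who never starts is a non-completer under any threshold of one session or more.

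**Conclusion.** The concern holds. The current text gives two different analysis sets with no rule for choosing, and following the opening rule for Hypothesis 2b would exclude people known to have 0 study-delivered sessions. Confidence in the inconsistency is high; its impact is conditional. Under the assumptions above, harm is nil at early losses of a few percent and becomes material only when loss differs between arms by about 10 points or more (false-positive rates of 11.3% to 17.1% against 5.5% at 50% true completion). Neither the size nor the direction of any bias can be determined from the documents. The repeated symptom outcomes are affected much less. It should be fixed before analysis.

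**What to change.** Delete the post-baseline requirement from the opening Data Analysis paragraph and state a single set: all randomised participants in their assigned arm. For Hypothesis 2b:

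- define attendance and completion as study-delivered CPT, and count every randomised participant;
- score those who never start CPT as 0 sessions and not completed;
- state the session count that defines completion;
- state in advance how homework is handled for those who never start (0 minutes is a choice, not a known value).

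For the repeated outcomes, keep participants with baseline data only in the likelihood model.

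This is a wording change that needs no new data and agrees with the plan's own intent-to-treat statement. The cost is a lower reported completion rate than the restricted set would give, if anyone would have been excluded. At 50% true completion the drop is 50/(1 − loss) − 50: 0.5 points at 1% early loss, 1.5 at 3%, 2.6 at 5%, 5.6 at 10% and 12.5 at 20%.

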Overview: The study is a randomized controlled trial (RCT) that will compare computerized EF training administered prior to CPT (CEFT-CPT) to a placebo word game training prior to CPT (WT-CPT). Goals of the research include 1) examining whether CEFT improves EF in OEF/OIF Veterans with PTSD and whether this in turn mediates PTSD symptom improvements, 2) investigating the efficacy of CEFT-CPT in improving treatment adherence, completion rates, and psychological and functional outcomes, and 3) determining whether baseline measures of EF predict treatment response. Veterans will be enrolled from the VASDHS system of PTSD clinics, spanning the main and 3 satellite facilities, and general outpatient mental health clinics. Assessments will be administered at baseline, immediately after CEFT or word training (prior to CPT), and after CPT completion.

Participants:

Inclusion criteria: 1) OEF/OIF Veterans enrolled at VASDHS, 2) aged 18-55 3) current PTSD diagnosis, 4) endorsement of cognitive complaints, 5) no pending medication changes, 6) English-speaking. Given the potential impact on outcome variables of interest, we will track current medication use in enrolled Veterans to ensure no recent or pending changes.

Exclusion criteria: 1) active substance use disorder in the last month, 2) suicidal intent or attempt within the last month, 3) schizophrenia, psychotic disorder and/or bipolar disorder, 4) dementia, 5) premorbid IQ < 70, 6) participation in other concurrent PTSD intervention studies, 7) previous completion of more than 4 CPT sessions, 8) history of a documented neurological disorder (e.g., Parkinson's disease, multiple sclerosis, epilepsy) 9) moderate to severe TBI (loss of consciousness greater than 30 minutes or post-traumatic amnesia greater than 24 hours).

Further exclusion criteria details: A history of mild TBI is highly comorbid in OEF/OIF but the majority of the literature supports a mental health etiology to persistent symptoms following mTBI; the current study will account statistically for mTBI history but it is not exclusionary.

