During recruitment, we will initially screen Veterans by phone. Those that are eligible for the study based on the phone screen will be brought to the lab for consenting, intake, and baseline assessments (approximately 200 Veterans). However, we assume a portion of those individuals will not qualify for the study. That will leave us with approximately 150 Veterans (75 per condition) to randomize to treatment. For recruitment, we will utilize the VASDHS system of PTSD clinics, spanning the main and 3 satellite facilities, and general outpatient mental health clinics. VA employees are not the target population, however they will not be excluded if they meet the inclusion criteria.

Financial Incentives: Participants will be compensated for their time after each completed assessment. Veterans will receive \$50 for the baseline assessment (\$30 for completion of the questionnaires and

neuropsychological assessment, \$20 for the fMRI assessment), \$30 as a bonus for completing at least 80% of the cognitive training (or placebo word games), \$50 for the post-computerized training assessment, and \$70 for the post-therapy assessment (Total possible = \$200).

Procedures:

Design and methods: Veterans will be randomized to either 12 weeks of CEFT-CPT or placebo word training plus CPT. Assessments will be administered three times: at baseline, immediately after CEFT or word training (prior to CPT), and after CPT completion. Assessment of PTSD diagnosis, symptom severity, quality of life, and subjective and objective measures of cognition will be administered at baseline (prior to computerized training onset), immediately after completing the cognitive training portion of the study (i.e., 6 weeks after baseline, just prior to starting CPT), and after completion of CPT treatment (approximately 6 weeks later, a total of 12 weeks after study initiation). Treatment satisfaction will be assessed after CEFT and CPT completion. Symptom severity will also be assessed at the midway point for the cognitive training and weekly during the CPT intervention component. Functional neuroimaging during rest and during two well-validated EF tasks will be collected at baseline, a Go-No Go Task that taps inhibition and an N-Back Task that taps working memory.

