Treatment Randomization: Following baseline assessment, participants will be randomized to the experimental (CEFT-CPT) or control condition (WT-CPT). A computer-generated randomization sequence will be provided by our statistical expert [name] (consultant). Randomization will be stratified by gender to ensure a balanced number of males and females are in each treatment group. Participants, the study assessor, and therapists will be blinded to the experimental treatment condition.

Post-Intervention Assessments (3-4 hours): The full battery of self-report questionnaires measuring psychiatric symptoms, quality of life, and subjective cognitive functioning, objective measures of neuropsychological functioning, and structured clinical interview for PTSD diagnosis will be re-administered twice, once after cognitive training completion and again after CPT completion. For the neuropsychological tests, alternate forms will be used where available and the RCT design will distribute any practice effects equally across the two groups. Participants will also complete the two EF tasks again that were administered at baseline during neuroimaging (though fMRI will not be collected again) or during the baseline assessment if they did not undergo fMRI for safety reasons.

Assessment Measures:

Symptom Measures:

- **PTSD:** The Clinician-Administered PTSD Scale DSM 5 (CAPS-5; Weathers et al., 2013) is the gold-standard, semi-structured interview that corresponds to DSM-5 criteria for PTSD. The CAPS-5 shows strong reliability and validity.

PTSD Checklist for DSM-5 (PCL-5; Weathers, Litz, Keane, Palmieri, Marx, & Schnurr, 2013) will be used to regularly assess PTSD symptomatology at several points throughout the study. The PCL-5 is a 20-item self-report measure of PTSD symptoms with good psychometric properties. The PCL-5 maps directly onto DSM-5 diagnostic criteria.

- **Depression:** Beck Depression Inventory-II (BDI-II; Beck, Steer, & Brown, 1996) is a 21-question multiple-choice self-report inventory, one of the most widely used instruments for measuring depressive symptoms.
- **Subjective day-to-day executive functioning:** Behavior Rating Inventory of Executive Function (BRIEF; Guy et al., 2004) is an ecologically sensitive 75-item self-report questionnaire that measures several aspects of EF in an individual's everyday life in the last month, including inhibition, shifting, working memory, planning/organizing, emotional control, etc.

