Optional measure: If there is any ambiguity in terms of psychiatric diagnoses based on the phone screen and a review of patient records (CPRS) that would disqualify the participant (i.e., schizophrenia, psychotic disorder, bipolar disorder, substance use disorder), the relevant portions of the MINI International Neuropsychiatric Interview (MINI; Sheehan, 2014) will be administered during the baseline assessment to clarify eligibility.

Objective neuropsychological testing: .

- **Tests of executive functioning:** Measures of inhibition, shifting/cognitive flexibility, and working memory include the Wisconsin Card Sorting Test (WCST; Heaton, 1981), Delis Kaplan Executive Function System (D-KEFS) Color-Word Interference Test and Trail Making Test (Delis, Kaplan, & Kramer, 2001), Paced Auditory Serial Addition Test (PASAT; Gronwall, 1977)
- **Verbal memory:** California Verbal Learning Test-II (CVLT-II; Delis, Kramer, Kaplan, & Ober, 2000)
- **Tests of attention and processing speed:** Wechsler Adult Intelligence Scale – IV (WAIS-IV) Digit Span, Digit Symbol, and Symbol Search subtests (Wechsler, 2008)
- **Premorbid intellectual functioning:** Wide Range Achievement Test, Fifth Edition (WRAT5) Reading subtest (Wilkinson & Robertson, 2017) [administered only at the baseline visit]
- **Tests of neuropsychological performance validity:** Test of Memory Malingering (Tombaugh, 1996) and an embedded measure within the CVLT-II (i.e., Forced Choice)

Other measures:

- **Quality of Life:** World Health Organization Quality of Life-BREF (WHOQOL-BREF; the WHOQOL Group, 1998) comprises 26 items, which measure the following broad domains: physical health, psychological health, social relationships, and environment.
- **Functional Impairment/Disability:** Inventory of Psychosocial Functioning (IPF; Rodriguez et al., 2012) is a self-report measure that assesses PTSD-related functional impairment across several domains, including relationships, work, education, self-care, etc.
- **TBI History:** Ohio State University TBI Identification Method - Interview Form (OSU TBI-ID; Corrigan & Bogner, 2007) is a short, structured interview that assesses TBI history and details about injury including cause, presence/minutes of loss of consciousness and post-traumatic amnesia, number of TBIs, etc. [administered only at the baseline visit]

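### Covariates are chosen by baseline significance tests, so neither the gender stratification factor nor mild TBI history has an assured place in the treatment models; the effect is modest and the remedy nearly free

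*Combined protocol and SAP*

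**What the plan says.** All places are in the combined protocol and SAP.

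- **Section 9, Data Analysis.** The rule covers gender, age, medications, depression and a group of TBI measures: "TBI-related variables will be examined for differences between groups at baseline; they will be added as covariates if differences are significant". No significance level is given, and the TBI measures are not listed.
- **Section 9, Treatment Randomization.** "Randomization will be stratified by gender to ensure a balanced number of males and females are in each treatment group". The method of allocation within strata, including any blocking, is not stated.
- **Section 9, Participants (further exclusion criteria details).** "A history of mild TBI is highly comorbid in OEF/OIF", and, with no condition attached, "the current study will account statistically for mTBI history but it is not exclusionary".
- **Section 9, Data Analysis (multilevel model).** Besides random effects, "the model will include the fixed effects of treatment group, time, and group-by-time interaction". Neither gender nor TBI history is named.
- **Section 9, Other measures (TBI History).** The baseline interview records "cause, presence/minutes of loss of consciousness and post-traumatic amnesia, number of TBIs, etc", so several variables could be tested.
- **Section 6, Hypothesis 2b.** Engagement is defined as "completing more hours of homework and attending a greater number of sessions"; completion rates are compared as well. These outcomes have no baseline value.

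**The concern.** Among all randomized patients, a significant baseline difference is a chance event. It says nothing about whether the variable predicts outcome, which is the reason to adjust. The rule also leaves the model unknown until the data are seen.

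Two variables show the difficulty. Stratification is there to keep gender balanced, yet gender is adjusted for only if that balance fails, and no other text puts it in the model. Mild TBI history is to be accounted for, yet the only procedure offered depends on a test that usually will not be significant. At stake are an analysis that does not reflect the randomization, a statement about mild TBI that may not be carried out, and possibly a little precision.

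**Working it through.** **Inputs.** From the documents: about 150 randomized, 75 per arm; gender strata; three assessment times ("Assessments will be administered three times: at baseline, immediately after CEFT or word training (prior to CPT), and after CPT completion"). Assumed, because the documents give no figure: two-sided alpha 0.05 for the baseline tests, 15 to 35 women among 150, mild TBI prevalence 20-70%, and the share of outcome variance explained. The plan has no figure on this point to reproduce.

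**1. Gender.** With blocks of 4, 8 or 10 within gender and 15, 25 or 35 women, the test was significant in 0 of 10,000 simulated lists at every setting. The bound explains why. The worst of these cases is 15 women in blocks of 10: one full block splits 5/5 and the remaining five may all go to one arm, giving 10 against 5. With 75 per arm,

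z = (10/75 - 5/75) / sqrt(0.10 × 0.90 × 2/75) = 0.0667 / 0.0490 = 1.36,

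which is below 1.96. If gender were re-tested after 20% or 50% random dropout (15% women, blocks of 4), it would enter in 0.03% or 0.8% of trials. Under simple randomization it enters in 4.7-5.4%.

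**2. Mild TBI, one yes/no variable.** Exact enumeration of two binomial arms of 75 gives entry in 4.9-5.5% of trials with the Pearson test (prevalence 20-70%) and 3.1-4.1% with Fisher's test (20-60%). A significant result needs a gap of about 1.96 × sqrt(p(1-p) × 2/75): 14.7 points at p = 0.3 and 16.0 at p = 0.5.

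**3. Several TBI variables.** The chance that at least one of k enters is 1 - 0.95^k if they are independent.

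| k | independent | correlation 0.6 | correlation 0.8 |
|---|---|---|---|
| 2 | 9.8% | 8.8% | 7.9% |
| 3 | 14.3% | 11.7% | 9.7% |
| 4 | 18.5% | 14.4% | 11.4% |

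Even with five independent variables at alpha 0.10, none enters in 0.90^5 = 59% of trials.

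**4. Type I error.** This uses a single-outcome linear model with 25 women and the rule applied to gender only (20,000 null trials, Monte Carlo SE about 0.15 points).

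| Variance explained by gender | Blocked strata | Simple randomization |
|---|---|---|
| 0% | 5.1% | 5.2% |
| 5% | 4.5% | 4.9% |
| 10% | 4.1% | 4.7% |

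The blocked column agrees with the approximation 2Φ(-1.96/sqrt(1-R²)), which gives 5.0%, 4.4% and 3.9%. The true variance of the arm difference is reduced by the balance on gender, but the unadjusted standard error does not reflect this. These figures carry over to group-by-time only in so far as gender predicts change.

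**5. Precision, outcomes without a baseline value.** Adjusting for two covariates with n = 150 multiplies the variance of the arm difference by about (1-R²)(1 + 2/145):

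| R² | Ratio | Change in variance |
|---|---|---|
| 0 | 1.014 | +1.4% |
| 1% | 1.004 | +0.4% |
| 5% | 0.963 | -3.7% |
| 10% | 0.912 | -8.8% |

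Break-even is at R² = 1 - 1/(1 + 2/145) = 1.4%.

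**6. Group-by-time.** With complete data, a covariate entered only as a main effect shifts a patient's whole profile and leaves the group-by-time estimate unchanged. Only a covariate-by-time term can alter that contrast.

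**The case against.** Three objections deserve an answer.

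**The harm is small.** This stands. A reader might infer that the rule biases the treatment effect or inflates Type I error. The documents do not support that: arms are formed by randomization, and the calculated error rates are at or below 5% within simulation error. Nor has a gain from adjustment been shown for the group-by-time test. Nothing in the documents shows that gender or mild TBI history predicts outcome or change, so adjustment could cost slightly more than it returns.

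**The two TBI statements can be read together.** A reader might infer that the plan contradicts itself, or has abandoned its commitment on mild TBI. That goes too far. Accounting for something statistically need not mean a covariate in every model, and the Data Analysis rule may be the intended means. What remains is that, on this reading, the accounting depends on a chance result of about one in twenty for a single variable, and the variable is undefined.

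**Imbalance need not be pure chance in the analysed set.** Data Analysis refers in one place to patients with a post-baseline evaluation and in another to everyone randomized. If the tests are run in the smaller set, differential dropout could contribute to an imbalance. That is a fair limit on the word chance, but a baseline significance test is not a sound remedy for dropout either.

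**Conclusion.** The point holds, with modest consequences. The rule selects covariates on something unrelated to their value, and no other text secures a place for gender or mild TBI history. That gender rarely enters does not depend on the unstated blocking, which only moves the figure between about 0% and about 5%. That mild TBI is usually left out holds for every assumed prevalence, for alpha 0.05 or 0.10, and for one to five variables.

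The cost is a data-dependent model, a somewhat conservative test if strata are blocked and gender is prognostic (for group-by-time, if it predicts change), and possibly a small loss of precision on sessions, homework and completion. The validity of the trial is not in question. The case for change is that a better rule is available with data already collected, not that the present one does serious damage.

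**What to change.** 1. Delete the baseline-significance rule and present baseline characteristics without tests.
2. Pre-specify gender and one defined mild TBI variable from the baseline interview (for example any mild TBI, yes/no) in the treatment-comparison models for hypotheses 1a, 2a and 2b. The grounds are that randomization uses the first and Section 9 commits to the second, not that either is known to be prognostic.
3. Where group-by-time is the test, include covariate-by-time terms.
4. Decide age, medications and depression in advance: list them as covariates or leave them out.
5. State whether the gender strata are blocked, and reconcile the Participants, Treatment Randomization and Data Analysis texts, including the list of fixed effects.

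**Cost.** No new data. With three categorical visits, each covariate adds one main effect and two time terms, so 2 × 3 = 6 parameters; the 2b models gain 2. For about 150 patients this is slight. If neither covariate is prognostic, outcomes without a baseline value carry about 1.4% more variance.
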